Aim 8: We will measure of retention in care (pharmacy refill and clinic attendance in last 6 months) and viral suppression (<200 copies/ml) comparing results from 6 months after randomization to 12 months after randomization. In addition, we will explore other factors based on modifiable variables in the SMART model including: adolescent peer support (Child and Adolescent Social Support Scale), (41) self-esteem (Rosenberg scale), (42) depression (PHQ-9), (43) and stigma (Internalized AIDS stigma scale), (44) connection to clinic (Working Alliance Inventory), (45) and transition readiness (HIV Adolescent Readiness for Transition). (46)

Aim 9: We will compare short term adherence (tenofovir levels) among adolescents in the InTSHA intervention group to the standard of care group. In addition, for viremic adolescents we will evaluate for the presence of HIV drug resistance searching specifically for Protease, Integrase, and Reverse Transcriptase mutations. We will use the Stanford database of HIV Drug resistance to determine significant HIV drug resistance mutations.

Modifiable factors from SMART model

- HIV knowledge
- Self-efficacy
- Beliefs
- Maturity
- Goals/Motivation
- Peer and social support
- Relationship with clinical staff
- Experience with HIV disclosure and stigma

Statistical methods

InTSHA: Interactive Transition Support for HIV-infected Adolescents Using Social Media - Detailed Protocol

Aim 1: We will use an inductive, content analytic approach to identify benefits and potential negative impacts of social media use during transition to adult care.(32, 51) Interviews will be translated from the local language (Zulu) into English and transcribed. Transcriptions will be uploaded, organized, and coded using Dedoose software (version 7.0.23, LA, California).(52) We will use open coding to inductively construct descriptive categories based on themes identified in the interviews. We will create a codebook based on themes identified in a subset of interviews. We will use an iterative process to construct categories based on the coded text. Broader themes will be created using linking and framing of coded text.

Aim 2: We will analyze the intervention development using the plan, engage, execute, reflect and evaluate process.(55, 56) We will then conduct the focus group based on the UTAUT model of technology acceptance to reflect on usefulness and acceptability the intervention.(57) The focus group discussions will evaluate the usability, challenges, and expectations of the intervention. The discussions will be recorded, transcribed, and translated into English. Transcriptions will be uploaded, organized, and coded using Dedoose software (version 7.0.23, LA, California).(52) We will then use an iterative process after each round of focus group session (adolescents, healthcare providers, and caregivers) to evaluate feedback for each version of the intervention based on coded themes identified during focus group feedback sessions. The intervention will subsequently be revised based on focus group feedback prior to demonstration with the next round of focus group participants. The final intervention will be based on the iterative process from all focus groups as well as input from our collaborative research team. To ensure fidelity of the intervention, we will use an intervention manual for content with training of the research team and healthcare providers. Only one team will monitor and facilitate the sessions.

Aim 3: Our primary focus is on estimating the acceptability and feasibility of the social media intervention for planning a larger clinical trial to measure efficacy. We will consider a feasibility / acceptability estimate of 80% or higher among the 40 participants as evidence that the social media program is acceptable to the population. Analysis. We will summarize the acceptability and feasibility data in the intervention group using standard summary statistics (e.g. counts/percentages; median and interquartile range of continuous measures). We will estimate the difference between the intervention group and the control for social support, connection to clinic, self-esteem, retention in care and virological suppression 6 months after randomization. The secondary outcomes will assist in planning a larger randomized clinical trial through a future R01 grant; the standard deviation for these differences is expected to be on the order of 8%. Depending on the number of individuals not retained in care or the number not virologically suppressed, we may use logistic regression to explore combinations of 2-3 variables potentially predictive of outcome. Assuming that the intervention is acceptable and feasible for participants, we would consider moving forward to an R01 if there was evidence of a benefit to participants, in terms of overall retention and virological suppression at 6 months, although we would not expect the difference to be statistically significant.

Power analysis (sample size, evaluable subjects, etc): With 40 participants in the experimental arm, if the true acceptability rate were 90% we would be able to rule out that acceptability was less than 70% with 90% power (alpha=0.05, one-sided) using an exact test.

Aim 4: We will use an inductive, content analytic approach to identify the different mechanisms of stigma and how they affect engagement in care during healthcare transition. Interviews will be recorded, transcribed, and translated into English. Transcriptions will be uploaded, organized, and coded using Dedoose software (version 7.0.23, LA, California).(52) We will use open coding to inductively construct descriptive categories based on themes identified in the interviews and then create a codebook based on themes identified in a subset of interviews. We will create categories based on the coded text using an iterative process and broader themes will be created using linking and framing of coded text.

Aim 5 and 7: We will analyze the stigma- and sexuality-focused interventions using the plan, engage, execute, reflect and evaluate process.(55, 56) We will then conduct the focus group based on the UTAUT model of technology acceptance to reflect on usefulness and acceptability of the

InTSHA: Interactive Transition Support for HIV-infected Adolescents Using Social Media - Detailed Protocol

intervention.(57) The focus group discussions will evaluate the usability, challenges, and expectations of the intervention. The discussions will be recorded, transcribed, and translated into English. Transcriptions will be uploaded, organized, and coded using Dedoose software (version 7.0.23, LA, California).(52) I will use an iterative process as described in Aim 2 after each focus group session with adolescents to evaluate feedback for each version of the stigma- and sexuality-based interventions based on coded themes identified during focus group feedback sessions. The content will be revised based on focus group feedback prior to demonstration with the second focus group. The final intervention content will be based on the iterative process from both focus groups, as well as input from our collaborative research team. We will train the research team using an intervention manual for content to ensure consistency of the intervention. Only one team will monitor and facilitate the sessions. Aim 6: We will summarize the sexual and reproductive health pre- and post- questionnaire data using standard summary statistics (e.g. counts/percentages; median and interquartile range of continuous measures). The questionnaire tests comfort with SRH topics in a uniformly negative (strongly disagree) to positive (strongly agree) 4 point Likert scale. We will estimate the difference in aggregate and question-specific score improvement between the intervention group and the control group in aggregate score on the questionnaire.

Aim 8: We will summarize viral suppression and retention in care in the intervention and control groups using standard summary statistics (e.g. counts/percentages; median and interquartile range of continuous measures). We will estimate the difference between the intervention group and the control for social support, connection to clinic, self-esteem, retention in care and virological suppression 12 months after randomization. The standard deviation for these differences is expected to be on the order of 8%. Depending on the number of individuals not retained in care or the number not virologically suppressed, we may use logistic regression to explore combinations of 2-3 variables potentially predictive of outcome.

Aim 9: We will summarize adherence (tenofovir levels) and significant HIV drug resistance in the intervention and control groups using standard summary statistics (e.g. counts/percentages; median and interquartile range of continuous measures). Although this study is not powered to detect a significant difference in the intervention and control arms for adherence or drug resistance, this will provide valuable explanatory detail for the primary results of this study.

VIII. Risks and Discomforts

Risk: Loss of privacy is a potential risk if information is compromised which could lead to unintended disclosure of personal medical information including HIV status.

Safeguard: The data from interviews and medical record review will be anonymous and identifiable information will not be recorded. All information will be stored on encrypted password-protected computers and loaded into a secure REDCap and Dedoose databases. Interviews will take place in a private setting. Participant names will not be recorded and personal identifiers will be limited to date of birth. Participants will be identified only by a unique study ID number. While the data is being collected, the list linking study ID numbers to patient file numbers (medical record numbers) will exist. This is necessary for cross-referencing the different data sources. Once all data has been collected, the list that links study ID numbers to medical record numbers will be permanently deleted. All steps in this de-identification process will occur on the password-protected, encrypted, study computer. Participants will be shown how to password protect their mobile phone. Only adolescents randomized to the intervention and study staff will have access to the social media site. Patient names or identifying information will not be used in online communications.

Risk: Loss of privacy including disclosure of HIV status during focus group discussions.

InTSHA: Interactive Transition Support for HIV-infected Adolescents Using Social Media - Detailed Protocol

Safeguard: Adolescents will be enrolled from Mahatma Gandhi Clinic and KwaMashu Poly Clinic. Current procedures at the clinic include attendance in an adolescent support group on clinic days. Since adolescents will be recruited from this site, they will already have interacted with each other during these group meetings as well as in the waiting room of the clinic. This will minimize accidental disclosure of HIV status among focus group members. In addition, we will review the importance of confidentiality within the focus group and that information discussed in the focus group should not be discussed outside of the focus group.

Risk: Loss of privacy including accidental disclosure of HIV status using social media.

Safeguard: Participants will be shown how to password protect their own mobile device. In addition, the majority of the content of the behavioral intervention will not involve HIV: self-efficacy, beliefs, maturity, goals/motivation, relationships, peer/social support. Any HIV-related content will not disclose individual's status. All activities involving HIV content will be scheduled; therefore, minimizing unexpected information arriving to mobile phones. Access to the social media discussion groups will be limited to study participants, their clinicians and research staff. Any breach of confidentiality or reported loss of protected health information will be reported to the clinical staff, Durban University of Technology and Partners IRB. Content will be suspended until an acceptable resolution has been determined by the IRB.

Risk: Guilt and Anxiety: One of the study components is an analysis of retention in care and viral suppression. The secondary outcome measures are retention in care and viral suppression, which can reflect default (loss to follow up) or virologic failure leading to feelings of guilt and anxiety.

Safeguard: Clinic staff will assist with contacting and finding those lost to follow up and adherence counseling will be available to those with virologic failure. These data will be de-identified following extraction. The interview component including information on retention and viral suppression for those identified as lost to follow up will be obtained prior informed consent.

Risk: A potential discomfort is anxiety, discomfort or fatigue during the interview. However, topics discussed are themes that are typically discussed in the clinical setting.

Safeguard: Trained adolescent counselors will be available after the interview session if required for any emotional distress. In addition, participants will be informed of their right to withdrawal from the study at any time.

Risk: Interviewing a vulnerable population that includes adolescents under the age of 18.

Safeguard: Minors under the age of 18 years (ages 15 to less than 18 years) will be offered assent to participate in the study. If they assent, then we will obtain informed consent from their caregivers. Adolescents under the age of 18 years who do not give assent to participate in the study will not be offered enrollment and their caregivers will not be contacted. Our research team has conducted more than 50 in depth interviews with adolescents less than 18 years old in similar settings.

Risk: Conflict between the adolescent and caregiver if both are enrolled, which may occur during the interview and consenting process.

Safeguard: Adolescents less than age 18 will provide assent to the study. Interviews will be conducted separately. Adolescents will be informed that their answers will not be shared with their caregivers. Caregivers will also be informed that their answers will not be shared with the adolescents.

Risk: Fear of impact on clinical care.

Safeguard: We will provide reassurance that responses or withdrawal from the study will not influence clinical care.

InTSHA: Interactive Transition Support for HIV-infected Adolescents Using Social Media - Detailed Protocol

Risk: Misuse of electronic social media, cyberbullying, spreading of false information, or loss of disclosure.

Safeguard: The social media site will be a closed group where access will only be granted by invitation. Only adolescents randomized to the intervention will have access. The research team will monitor the site and any messages that are deemed inappropriate will be deleted.

Risk: Inducement to participate through provision of money for data (air time).

Safeguard: Participants will receive funds to cover the cost of their data to participate in the study. We will work with the local IRB, local clinical staff, caregivers and adolescents in Aim 1 to address concerns about coercion to participate in the research study by provision of money for data use.

Risk: Interference with clinical staff time

Safeguard: We will use research staff to monitor activity on the social media site. Clinical staff will participate at scheduled intervals. Currently the clinical staff spends two hours weekly involved in the adolescent support group; however, the activities are often poorly organized and lack focus. We will re-purpose, focus, and organize some of this time to include time involved in the social media intervention.

IX. Potential Benefits

Although, there is no direct benefit to the individual during the study, results of this research may assist in the development of methods to improve adolescent HIV care and transition to adult care. In addition, participants will be given 250 Rand (~\$20 USD) to compensate them for their time spent doing the interviews, focus groups and completing the surveys.

Adolescents in Aim 3 will receive funds to compensate them for data use and air time for their cell phones. This will average approximately 20 USD per month. See protection against inducement above.

Adolescents in Aims 4, 5 and 7 will be given approximately 20 USD to compensate them for their time spent doing the stigma-related interviews and focus groups.

We feel the risks associated with the study are small. The benefits are consistent with cultural expectations and they follow the established standard with IRB approval in our other studies. We therefore believe the balance of benefit and risk is appropriate.

Potential benefits to society

Retention in care and viral suppression among HIV-infected adolescents transitioning to adult care are important for perinatally-HIV infected adolescents. Effective strategies to enhance retention in care and viral suppression among adolescents during transition to adult care are needed. Using social media to address the modifiable factors in the SMART model may improve retention and viral suppression rates among adolescents living with HIV as they transition to adult care. In addition, the knowledge gained in this study will assist with the development and evaluation of new interventions to address this vulnerable population.

X. Monitoring and Quality Assurance

Independent monitoring of source data

Data extracted from the clinic records will be reviewed by a second staff member for completeness and accuracy.

Transcriptions will be reviewed by two independent researchers for the development of themes.

Safety monitoring (DSMB)

InTSHA: Interactive Transition Support for HIV-infected Adolescents Using Social Media - Detailed Protocol

[name] will be responsible for oversight of the research activities and data collected at Mahatma Gandhi Hospital and KwaMashu Poly Clinic. [name] and [name] will communicate frequently with Drs. [name] and [name] and [name], as well as other study staff, by email and Skype (at least weekly). [name] will make study site visits at least twice annually, while [name] will make a site visit annually. All serious adverse events will be reported to the Mahatma Gandhi Hospital and KwaMashu Poly Clinic clinical staff, University of KwaZulu-Natal Bioethics Review Committee and Partners Ethics Review Committee according to their requirements (generally 7-10 days). Data collection will be suspended until appropriate precautions have been taken to avoid repeat safety concerns.

XI. References

1. UNAIDS. UNAIDS Country Report: South Africa. 2015.
2. UNAIDS. Global Report: UNAIDS Report on the Global AIDS Epidemic 2013. Joint United Nations Programme on HIV/AIDS; 2013.
3. Adolescents PoAGfAa. Guidelines for the use of antiretroviral agents in HIV-1-infected adults and adolescents. In: Services. DoHaH, editor. Available at <http://www.aidsinfo.nih.gov/ContentFiles/AdultandAdoles2015>.
5. Life expectancy of individuals on combination antiretroviral therapy in high-income countries: a collaborative analysis of 14 cohort studies. Lancet. 2008;372(9635):293-9.
6. Transitioning HIV-infected youth into adult health care. Pediatrics. 2013;132(1):192-7.
7. Andiman WA. Transition from pediatric to adult healthcare services for young adults with chronic illnesses: the special case of human immunodeficiency virus infection. The Journal of pediatrics. 2011;159(5):714-9.
9. WHO. HIV and Adolescents: Guidance for HIV Testing and Counselling and Care for Adolescents Living with HIV. Geneva, Switzerland: World Health Organization; 2013.

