Aim 7: Qualitatively assess individuals' experiences with sexual and reproductive health. We will conduct in-depth interviews with a convenience sample of up to 20 intervention participants (until saturation is met) using an in-depth interview guide based on the Theory of Planned Behavior. The 60 minute interviews will cover individuals' sources of knowledge about sex and sexuality, perceptions of social norms, personal relationship experiences, communication about sex with others, and thoughts and critiques of the INTSHA sexual and reproductive health module. The interviews will be recorded, transcribed, translated, and thematically analyzed using Dedoose. Combined with Aim 6, these results will inform the efficacy of mHealth in changing attitudes about sexual and reproductive health in adolescents living with HIV.

Aim 8: Evaluate the impact of the InTSHA intervention 12 months after randomization in the clinical trial.

InTSHA: Interactive Transition Support for HIV-infected Adolescents Using Social Media - Detailed Protocol

Aim 9: Determine the long-term impact of InTSHA on ART adherence and HIV drug resistance among adolescents transitioning to adult care.

III. Subject Selection

a. Inclusion/exclusion criteria

Inclusion Criteria:

Adolescent participants (Aims 1-7) will meet the following criteria: 1. Aged 15 to 19 years; 2. Perinatally HIV-infected; 3. Receiving ART for at least 6 months; 4. Fully aware of their HIV status.

Caregiver participants (Aim 1) will be the self-defined primary caregivers of the adolescents transitioning to adult-based self-care.

Healthcare providers (Aims 1 & 2) will be South African adult and pediatric physicians, counselors, nurses, and psychologists who care for adolescents living with HIV before or after transition to adult care.

Exclusion Criteria (all participants): Inability to read and/or speak English or Zulu or severe mental or physical illness preventing informed consent.

IV. Subject Enrollment

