Aims 8/9: We will offer enrollment to the 80 participants already enrolled in the InTSHA study. Participants will attend one additional research visit at least 12 months after completion of the intervention in the intervention group and 12 months after randomization for the control group. During the visit, participants will complete a follow-up questionnaire and have a blood draw. All participants will have a viral load assessment.

V. Procedures for obtaining informed consent (including timing of consent process)

Aims 1-2 and 4-7: Since adolescents in South Africa do not require parental/caregiver consent for clinical care, many of them attend clinical appointments without an adult caregiver present. We will offer enrollment to unaccompanied minors ages 15 to 18 if they are interested. With their assent, we will contact their caregiver via telephone to obtain telephone consent with the assistance of the attached telephone consent script. If the adolescent is accompanied by an adult caregiver, a trained research assistant fluent in English and Zulu will obtain written consent from guardians in Zulu or English for adolescents aged less than 18 years old and assent from the adolescent participants. Written assent will be obtained from all participants under the age of 18 years. Informed consent from caregivers will be obtained for the prospective implementation of all proposed study protocols for adolescents less than 18 years old that have given assent to participation either in person or via telephone. Adolescents under the age of 18 years who do not assent to participate in the research will not be able to participate. Adolescents 18 years old or older will provide their own consent.

Aim 3,8,9: Since this is an intervention study, we will require written assent from all participants under the age of 18 years. Informed consent from caregivers will be obtained for the prospective implementation of all proposed study protocols for adolescents less than 18 years old that have given assent to participation either in person or via telephone. Adolescents under the age of 18 years who do not assent to participate in the research will not be able to participate. Adolescents 18 years old or older will provide their own consent. For aims 8 and 9 participants will be asked to re-consent to be in the extended study.

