Aim 6: The same subjects enrolled in Aim 3 will be provided with a pre- and post- intervention questionnaire. During visit one, we will collect data on an additional 9 questions about consent, contraception, family planning, social pressures, and communication related to SRH. The second research visit will take place 6 months after randomization, after the intervention has been completed, to assess changes in beliefs and attitudes towards SRH over time.

Data to be collected and when the data is to be collected

InTSHA: Interactive Transition Support for HIV-infected Adolescents Using Social Media - Detailed Protocol

An additional 9 questions about attitudes and beliefs on SRH will be collected by adding to the existing pre and post questionnaire.

Aim 7: We will recruit participants from adolescents who participated in the clinical trial in Aim 3 from Mahatma Gandhi Hospital's and KwaMashu Poly Clinic's Pediatric and Adult HIV Clinics. Adolescent participants will be identified and referred by the hospital clinicians after clinic visits. We will conveniently sample up to 20 adolescents (based on saturation of major themes) who completed the intervention. We will attempt to enroll equal number of male and female participants of varying ages. Interviews will be conducted in isiZulu or English and last about 1 hour. **Measures:** The in-depth interviews will evaluate personal experiences with sexual and reproductive health as adolescents living with HIV based on the Theory of Planned Behavior and how our mobile health intervention affected attitudes and beliefs of sexual and reproductive health. We will aim for thematic saturation in each group.

Aims 8: We will recruit only patient previously enrolled in the InTSHA study. Participants will complete the same follow-up questionnaire that was completed at the end of the study. Participants will have a single blood draw to evaluate long term viral suppression.

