Aim 9: All participants will have a single additional research visit as in Aim 8. Participants will have a single blood draw (same as aim 8) to evaluate tenofovir levels and for HIV genotyping to evaluate for drug resistance in those individuals with viremia. Samples from individuals with a detectable viral load >500 copies/ml will be sent for genotype analysis. We will attempt to perform HIV-1 genotype analysis for those with low level viremia with viral loads between 200 and 500 copies/ml; however, amplification of the HIV genome may not be possible with low level viremia. For participants with undetectable viral loads, development of HIV drug resistance is not a concern.

VII. Biostatistical Analysis

Study Endpoints:

Outcomes:

Aim 1: The in-depth interviews will evaluate the current use of social media and its impact on modifiable factors in the SMART model as indicated in **Table 5**. We will aim for thematic saturation in each group.

Table 5. Interview Domains

Optimal platforms

- WhatsApp, Facebook, Snapchat, MIXIT to determine acceptability, usability, flexibility, data requirements

Social media issues

- Social media use
- Security
- Privacy of cellular phone and online data
- Cyber bullying

InTSHA: Interactive Transition Support for HIV-infected Adolescents Using Social Media - Detailed Protocol

Aim 2: I will then use an iterative process after each round of focus group session (adolescents, healthcare providers, and caregivers) to evaluate feedback for each version of the intervention based on coded themes identified during focus group feedback sessions. The intervention will subsequently be revised based on focus group feedback prior to demonstration with the next round of focus group participants. The final intervention will be based on the iterative process from all focus groups as well as input from our collaborative research team.

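### The single Aims 8/9 visit is timed from end of intervention in one arm and from randomization in the other, so the intervention arm cannot be seen at Aim 8's stated 12 months after randomization

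*Combined protocol and SAP*

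**What the plan says.** Four parts of the protocol bear on when the long-term comparison is made.

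- Section II, Aim 8, states the objective: "Evaluate the impact of the InTSHA intervention 12 months after randomization in the clinical trial".
- Section VII, study endpoints for Aim 8, describes retention and viral suppression "comparing results from 6 months after randomization to 12 months after randomization". It does not mention arms.
- Section VII, statistical methods for Aim 8, plans the between-arm difference in the questionnaire scales and in "retention in care and virological suppression 12 months after randomization".
- Section IV, Aims 8/9, schedules the visit "at least 12 months after completion of the intervention in the intervention group and 12 months after randomization for the control group".

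Only one such visit exists. Section VI says of it, for Aim 8: "Participants will have a single blood draw to evaluate long term viral suppression". For Aim 9 it says: "All participants will have a single additional research visit as in Aim 8".

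The length of the intervention is not given as a number. The nearest statement is under Aim 6 in Section VI: "The second research visit will take place 6 months after randomization, after the intervention has been completed". The Aim 9 objective has no numerical time point: "Determine the long-term impact of InTSHA on ART adherence and HIV drug resistance among adolescents transitioning to adult care".

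**The concern.** Randomization makes the arms comparable at equal time since randomization. Section IV gives the arms different clocks. The intervention clock starts only when the intervention ends, while the control clock starts at randomization. Two things follow.

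First, the Aim 8 estimate cannot be made at its stated time for anything measured at the visit, namely viral load and the questionnaire scales. No other visit can supply month-12 values.

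Second, if controls are seen at month 12, visit time is determined by arm. Any change over time that both arms share would then enter the between-arm difference and could look like an intervention effect or conceal one. With no overlap in visit times, adjustment could not separate the two without an outside assumption about the trend. The protocol states neither a visit window nor an adjustment.

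Aim 9 does not contradict itself, because it names no time point. Its tenofovir and resistance comparisons use the same blood draw, however, and can share the imbalance.

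**Working it through.** **Inputs**

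- Stated time of the Aim 8 comparison: month 12 after randomization (Sections II and VII).
- Visit rule: at least 12 months after completion for the intervention arm, 12 months after randomization for controls (Section IV).
- d = months from randomization to completion of the intervention. This is not stated. It is above zero, since Section IV (Aim 6) refers to a final session and Section IX budgets phone data by the month. The Aim 6 text in Section VI puts completion by about month 6. Assumed values: 1, 3 and 6.

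**Step 1: does the stated time reproduce?** Control visit = 12, which matches. Earliest intervention visit = 12 + d, which equals 12 only if d = 0. The stated time is not reproduced in the intervention arm.

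**Step 2: size if only the intervention arm has an open-ended minimum and controls are seen at month 12.** Gap ≥ d. Interval since the 6-month visit ≥ 12 + d − 6 = 6 + d, against 12 − 6 = 6 in controls.

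| Assumed d | Earliest intervention visit | Control visit | Minimum gap | Interval since month 6, intervention vs control |
|---|---|---|---|---|
| 1 | 13 | 12 | 1 | at least 7 vs 6 |
| 3 | 15 | 12 | 3 | at least 9 vs 6 |
| 6 | 18 | 12 | 6 | at least 12 vs 6 |

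**Step 3: size if the minimum also covers controls.** Controls may then be seen later than month 12, so the gap can be zero. The earliest time common to both arms is 12 + d = 13, 15 or 18. Month 12 is still excluded, and nothing in the text aligns the arms.

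**Step 4: retention.** Section VII uses a 6-month look-back. Counted back from the earliest intervention visit it covers months 6 + d to 12 + d, against 6 to 12 for controls seen at month 12. The overlap is max(0, 6 − d) = 5, 3 or 0 months for d = 1, 3, 6. This arises only if the look-back runs from the visit date. Retention comes from pharmacy and clinic records and can instead be fixed at month 12 in both arms.

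**Step 5: who could still be seen at month T.** Aims 8/9 are offered to the 80 participants already in the trial, and recruitment was planned over 15 months (Section VI, Aim 3). Assume even enrolment and visits starting t months after the last randomization. The share already past month T is max(0, min(1, (15 + t − T)/15)).

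| t | Past month 12 | Past month 18 |
|---|---|---|
| 0 | 3/15 = 20%, 16 of 80 | 0 |
| 3 | 6/15 = 40%, 32 of 80 | 0 |
| 6 | 9/15 = 60%, 48 of 80 | 3/15 = 20%, 16 of 80 |

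These counts bear on the choice of remedy, not on whether the conflict exists.

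**The case against.** The strongest reply is that a full year after the intervention ends may be a deliberate durability question, and that the minimum may be meant for both arms. Step 5 supports the second point: if many participants are already past month 12, many controls could not be seen then either, so a flexible minimum for everyone is the more workable reading. On that reading a gap between arms is possible but not certain. This stands, and it limits how firmly bias can be asserted. It does not rescue the stated time point, because month 12 remains out of reach for the intervention arm. If a year after completion is intended, Sections II and VII are the parts that need changing, and controls still need a visit at the same time since randomization.

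The reach is also limited. Aim 8 is a descriptive extension of an 80-person pilot, and the plan says the study is not powered for Aim 9's adherence and resistance comparisons. The primary outcomes, the 6-month comparison and the decision to seek a larger grant, which Section VII ties to 6-month results, are untouched. This too stands. Small size, though, does not justify an estimate that cannot be made at its labelled time.

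Finally, the enrolment counts rest on even recruitment, a planned duration and an assumed start date for visits, and they ignore dropout and re-consent. They are illustrative only.

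**Conclusion.** The concern holds and should be fixed. Followed as written, Section IV puts every intervention participant past the month-12 point that Sections II and VII give for Aim 8, for any d above zero. Confidence in that contradiction is high.

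The size depends on d, which is assumed. The earliest intervention visits fall at month 13 to 18 for d of 1 to 6. The gap from controls is at least d if controls are seen at month 12, and it may be zero at a later common time if the minimum applies to both arms. The size and direction of any bias in viral suppression or the questionnaire scales cannot be worked out from the documents, which give no time trend. Retention is affected only if its window is counted from the visit. Aim 9 has no conflict in its text but can share the imbalance.

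**What to change.** Reconcile Section IV with Sections II and VII by using time since randomization as the single anchor, with the same visit window in both arms. Before choosing the time, count how many enrolled participants in each arm are already past month 12. Then take one of two options:

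- **Keep month 12.** This matches the Aim 8 text, but it shortens follow-up after the intervention and may miss those already past the window: about 16, 32 or 48 of 80 under the assumptions in the working.
- **Use a later common time** in both arms and restate the Aim 8 time point. Month 18 would allow a year after completion for d up to 6 and would miss about 0, 0 or 16 under the same assumptions. It delays control visits by 6 months.

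In either case, take retention from records over the same window since randomization in both arms, and report actual visit times since randomization by arm for Aims 8 and 9. The cost is a text change and rescheduling; no visits are added.
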